ADA: antidrug antibody; AE: adverse event; CxDx: Cycle x Day x; cfDNA, cell-free DNA; CT: computed tomography; CTCs: circulating tumor cells; d: day(s); ECG: electrocardiogram; ECOG: Eastern Cooperative Oncology Group; EOT: end of treatment; ICF: informed consent form; IRR: infusion-related; RECIST: Response Evaluation Criteria in Solid Tumors; MRI: magnetic resonance imaging; OS: overall survival; PD: progressive disease; PFS: progression-free survival; PK: pharmacokinetic(s); Q3W: once every 3 weeks; Q12W: once every 12 weeks; QTc: corrected QT interval; RBC: red blood cell; SAE: serious adverse event; SOE: Schedule of Events; TBNK: quantification of T cells (including CD4+ and CD8+ T cells), B cells, and natural killer cells; TSH: thyroid-stimulating hormone;

CONFIDENTIAL

WBC: white blood cell.

Crosses in parentheses “(X)” indicate tests are to be performed only under certain circumstances as indicated in associated footnote(s).

- ^a Written informed consent must be obtained before performing any protocol-specific procedure. Test results from routine clinical management are acceptable for screening if obtained within the specified time window. The screening period is 21 days and runs between ICF signature and first dose unless it is explicitly specified otherwise.
- ^b For all participant patients in the trial, QTc duration should be assessed locally with 1 standard local ECG to be collected and read at screening, at predose and at the end of modakafusp alfa infusion (+ 30 minute window) of C1D1, C2D1 and C3D1, and at EOT. Additional ECGs may be obtained as clinically indicated at any time during the study at the discretion of the investigator. During the safety lead-in dose expansion phase, triplicate ECGs will be obtained as described in these SOEs and in [Table 16.g](#). When the timing of triplicate and single (safety) ECGs coincide, the site can use the triplicate ECG collection for safety evaluation.
- ^c Vital signs will be measured before starting the infusion and after the completion of the infusion. Vital signs include temperature, pulse, respiratory rate, oxygen saturation, and blood pressure. Blood pressure will be measured every 30 minutes (± 5 minutes) during the first 4 infusions, after the end of the infusion, and at any moment if the patient complains of symptoms consistent with an IRR. If the patient experiences hypotension (with or without symptoms), intensive blood pressure monitoring according to local practice should be instituted. The patient cannot be released from the site until blood pressure has returned to Grade 1 or baseline for at least 1 hour. During the first infusion and for 6 hours postinfusion in the first 2 treatment cycles, patients should be continually monitored by medically qualified staff with access to emergency medical equipment and medications to manage IRRs. In Cycle 3 and beyond, patients should be continually monitored for at least 2 hours before the end of infusion, and the monitoring duration could be extended per a patient’s prior dosing experience.
- ^d In case of an IRR, blood draws should be performed for central evaluation of cytokines, chemokines, complement, immune complex formation and ADAs. The following samples should be collected: serum sample for circulating biomarkers and serum sample for immunogenicity.
- ^e The recommended pembrolizumab dose of 400 mg will be administered as an IV infusion over 30 ± 10 minutes Q6W. Pembrolizumab will be administered before modakafusp alfa on days when both modakafusp alfa and pembrolizumab are given. At least 30 minutes should elapse between the completion of the infusion of the pembrolizumab and the infusion of modakafusp alfa.
- ^f CT and/or MRI scans of the chest, abdominal cavity, and pelvis should be acquired with at least IV contrast. The imaging modalities used for a patient should remain consistent throughout the study. If IV contrast-enhanced CT scans are contraindicated for a particular patient, a noncontrast-enhanced CT of the chest should be acquired in addition to an oral contrast-enhanced CT of the abdomen and IV contrast-enhanced pelvic MRI. At present, low-dose or attenuation correction CT portions of a combined PET-CT are of limited use in anatomically based efficacy assessments, and it is therefore suggested that they should not be substituted for dedicated diagnostic contrast-enhanced CT scans for anatomically based RECIST measurements. However, if a site can document that the CT performed as part of a PET-CT is of identical diagnostic quality to a diagnostic CT (with IV and oral contrast), then the CT portion of the PET-CT can be used for RECIST measurements. Note, however, that the PET portion of the CT introduces additional data that may bias an investigator if it is not routinely or serially performed. Repeat CT and/or MRI scans should be performed every other cycle up to Cycle 7 (Day 1 [-7 days] of Cycles 3, 5, and 7), every 3 cycles thereafter, and as clinically indicated. Response will be determined locally according to RECIST v1.1 (see Section [9.3.14.1](#)). Screening and on-treatment images, when available, should be submitted to the imaging core laboratory vendor for retrospective central reading when it is required. Clinical decisions will be made per local response assessment. Availability of prescreening scan(s) is not a prerequisite for study eligibility (Section [9.3.14.2](#)). If available, the most recent prescreening diagnostic quality CT and/or MRI scans dated within 3 months before the planned first dose of modakafusp alfa should be submitted to the imaging core laboratory vendor for tumor growth rate determination. The date of the scan should be indicated. Response assessment will be calendar-based regardless of treatment delays/interruptions.

- ^g Chemistry will include tests listed in [Table 9.a](#). Chemistry on C1D15 and C3D15 could be assessed in a local hospital if there is no planned PK sampling on those visits per [Table 16.g](#) and [Table 16.h](#).
- ^h Hematology will include tests listed in [Table 9.a](#). Hematology on C1D15 and C3D15 could be assessed in local hospital when there is no planned PK sampling on those visits per [Table 16.g](#) and [Table 16.h](#).
- ⁱ *Footnote no longer applicable.*
- ^j Urinalysis (dipstick) will include tests listed in [Table 9.a](#). Microscopic if clinically indicated only: bacteria, RBCs, WBCs, casts, and crystals.
- ^k A serum or urine pregnancy test will be performed for patients of childbearing potential with negative results during screening and again at C1D1 (baseline) if the screening test was performed more than 72 hours before the C1D1 dosing. A serum or urine pregnancy test must be performed at predose (within 72 hours prior to dosing) on Day 1 of each cycle with negative results available before modakafusp alfa is administered. A serum or urine pregnancy test is required at EOT.
- ^l Immunosafety lab tests include thyroid-stimulating hormone (TSH), free thyroxine (free T4) and cortisol (morning preferred) repeated every other cycle starting from Cycle 3, and at the EOT as detailed in [Section 9.3.13.3](#). These tests are analyzed locally.
- ^m A minimum of 1 target lesion for response assessment is required for enrollment in phase 2. A separate lesion amenable for biopsy is required for enrollment in cohort I and II (post fertility analysis) and cohort III (all patients, inclusive of safety-lead in) of phase 2. New (fresh) biopsies at screening and on treatment will be required for all patients in cohort III (safety-lead in and expansion) of phase 2. For patients in cohorts I and II of phase 2, new (fresh) screening and on-treatment biopsies will be optional up until fertility has been met. Once fertility has been met for either cohorts I or II, new (fresh) biopsies will be required at screening and on-treatment. See [Section 9.3.15.2](#) for details. The accessible lesion for biopsy should not have been previously irradiated or designated as the only target lesion for measurable disease.
- ⁿ Blood samples for modakafusp alfa PK and pembrolizumab PK will be collected at time points specified in [Table 16.g](#) and [Table 16.h](#) below.
- ^o Flow cytometry methodologies will be used to immunophenotype T, B, and NK lymphocyte subsets, and will be analyzed centrally.
- ^p Predose.
- ^q Predose and at 4 hours (+/- 30 minutes) after the end of infusion.
- ^r Blood samples for immunogenicity (ADA) testing will be collected before the dose on Day 1 of every cycle while the patient remains in treatment and, if possible, at the EOT follow-up visit. In case of an IRR, blood draws should be performed for central evaluation of immunogenicity.
- ^s One blood sample for DNA will be taken at either screening or C1D1 predose (when it is not possible to collect at screening, samples can be collected at the next visit).
- ^t Patients who discontinue modakafusp alfa for reasons other than PD will continue PFS follow-up every 12±1 weeks from the EOT visit until the occurrence of PD, death, the start of subsequent systemic anticancer therapy, study termination, or until 6 months after the discontinuation of study treatment, whichever occurs first. PFS will be assessed according to RECIST v1.1.
- ^u Patients will be followed for survival every 12±1 weeks until death, loss to follow-up, consent withdrawal, or study termination. Survivor information and death details may be collected by methods that include, but are not limited to, telephone, e-mail, mail, or retrieval from online or other databases (eg, Social Security indexes). In addition, the start of another anticancer therapy for the disease under study will be collected.
- ^v A sample for blood typing to be taken only at screening. Blood banks need to be alerted that the patient is going to receive an anti-CD38 antibody that may interfere with blood typing in a manner similar to daratumumab. If the blood bank issues a compatibility card, it should be made available to the patient. The patient needs to tell other healthcare providers that he/she is receiving an anti-CD38 antibody if, for example, a blood transfusion is needed.
- ^w A whole blood sample will be collected to quantify CTCs at baseline and correlate with response.

- ^x Pharmacodynamic samples to be collected for patients enrolled within the safety lead-in and those enrolled within the expansion cohorts prior to futility being met.
- ^y After futility has been met within an expansion cohort, the on-treatment biopsy sample should be taken prior to Cycle 3 administration of modakafusp alfa and pembrolizumab. For convenience, biopsy can be taken up to a 7 days prior to C3D1, preferably to coincide with imaging assessments of disease.

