8.0 STUDY DRUG

8.1 Study Drug Administration

All protocol-specific criteria for administration of study drug must be met and documented before drug administration. Study drug will be administered only to eligible patients under the supervision of the investigator or identified subinvestigator(s).

The initial dose should be based on a patient's weight at screening and only adjusted if there is a $\geq 10\%$ change in body weight.

Investigational sites should refer to the pharmacy manual for preparation of each dose. Modakafusp alfa doses < 1.5 mg/kg will be administered over 1 hour (± 10 minutes). Modakafusp alfa doses ≥ 1.5 mg/kg will be administered over 2 hours (± 10 minutes) and could be extended to 4 hours at the investigator's discretion. Any decrease in infusion duration must be discussed with and agreed upon by the sponsor. If a patient presents with an infusion-related reaction at any dose level, the duration of the infusion may be extended per investigator's discretion. Total time from modakafusp alfa dosing solution preparation until end of infusion must not exceed 7 hours.

In the combination treatment cohorts, the recommended pembrolizumab dose of 400 mg will be administered as an IV infusion over 30 ± 10 minutes Q6W in combination with modakafusp alfa. Please see premedication and observation guidelines in Section 8.8.1.

Pembrolizumab will be administered before modakafusp alfa on days when both modakafusp alfa and pembrolizumab are given. At least 30 minutes should elapse between the completion of the infusion of the first study drug and the initiation of the infusion of the second study drug.

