8.8 Permitted Concomitant Medications and Procedures

8.8.1 Premedication

Due to the occurrence of Grade 2 IRRs in 8 of 17 patients receiving modakafusp alfa at doses of 0.1 to 1.5 mg/kg Q3W in the current study as of the data cutoff of 23 January 2021, the following list of medications are mandatory in all cycles before infusion of modakafusp alfa to prevent and/or mitigate this potential AE.

1. Corticosteroid IV or orally (PO) (dexamethasone 10 mg to 20 mg or equivalent) 60 minutes to 2 hours before treatment.
2. Acetaminophen 650 mg to 1000 mg PO 60 minutes to 2 hours before treatment.
3. Diphenhydramine or equivalent 25 mg to 50 mg PO approximately 1 hour before treatment.

Montelukast may be given to patients who are intolerant to diphenhydramine or for whom diphenhydramine is ineffective. Additional premedications of nonsteroidal anti-inflammatory drugs (NSAIDs) and H₂ blockers could be added per investigator's discretion.

Medication(s) shall be administered according to medical standards and at sufficient time prior to start of infusion of modakafusp alfa that allows the premedication drugs to exert their effects.

For the phase 2 expansion phase, the history of IRR to prior CPI treatment will be collected.

During the infusion and for 6 hours post-infusion in the first 2 treatment cycles, patients should be continually monitored by medically qualified staff with access to emergency medical equipment and medications to manage IRRs. In Cycle 3 and beyond, patients should be continually monitored for at least 2 hours post the end of infusion, and the monitoring duration could be extended per a

patient's prior dosing experience. Potential IRRs shall be managed as medically indicated including, but not limited to, repeated administration of drugs described above.

For details about treatment of IRRs, please refer to Section 8.10.1. Procedures for reporting AESIs are described in Section 10.2.1.

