9.3 Study Procedures

Sites will make every effort to see patients in the clinic to complete all study-specified assessments as outlined in the SOE ([Appendix A](#)). In unavoidable circumstances, such as the COVID-19 public health emergency, exceptions can be made for alternative methods for conducting patient visits

and performing laboratory and imaging assessments as detailed below. Remote visits and telemedicine must comply with national and local laws and regulations. Such instances will be documented in the study records and electronic case report form (eCRF) if applicable, and the sponsor will be informed.

Refer to the SOE ([Appendix A](#)) for timing of assessments. Additional details are provided as necessary in the sections that follow. Evaluations during the screening period are to be conducted within 21 days before administration of the first dose of the study drug. Some procedures conducted during the screening period that are performed within 4 days of C1D1 may also be used as the predose evaluation and do not need to be repeated, unless otherwise specified.

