^a Written informed consent must be obtained before performing any protocol-specific procedure. Test results from routine clinical management are acceptable for screening if obtained within the specified time window. The screening period is 21 days and runs between ICF signature and first dose unless it is explicitly

specified otherwise.

- ^b For all participant patients in the trial, QTc duration should be assessed locally with 1 standard local ECG to be collected and read at screening, at predose of C1D1 and C2D1, and at EOT. Additional ECGs may be obtained as clinically indicated at any time during the study at the discretion of the investigator. Triplicate ECGs will be obtained as described in these SOEs and in [Table 16.f](#). When the timing of triplicate and single (safety) ECGs coincide, the site can use the triplicate ECG collection for safety evaluation.
- ^c Vital signs will be measured before starting the infusion and after the completion of the infusion. Vital signs include temperature, pulse, respiratory rate, and blood pressure. Blood pressure will be measured every 30 minutes (± 5 minutes) during the first 4 infusions, after the end of the infusion, and at any moment if the patient complains of symptoms consistent with an IRR. If the patient experiences hypotension (with or without symptoms), intensive blood pressure monitoring according to local practice should be instituted. The patient cannot be released from the site until blood pressure has returned to Grade 1 or baseline for at least 1 hour. During the infusion and for 6 hours postinfusion in the first 2 treatment cycles, patients should be continually monitored by medically qualified staff with access to emergency medical equipment and medications to manage IRRs. In Cycle 3 and beyond, patients should be continually monitored for at least 2 hours after the end of infusion, and the monitoring duration can be extended per a patient's prior dosing experience.
- ^d In case of an infusion reaction of Grade ≥ 2 , blood draws should be performed for central evaluation of immune markers, cytokines, chemokines, and ADAs. The following samples should be collected: serum sample for circulating biomarkers, and serum sample for immunogenicity.

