Table 16.h Sparse Serum PK Sampling Schedule to Characterize PK of Modakafusp Alfa and Pembrolizumab During Phase 2 Expansion Phase (excluding Safety Lead-In Periods)

	Cycles 1 and Beyond	
	Day 1	
	Modakafusp Alfa PK ^a	Pembrolizumab PK ^c
Predose (within 30 min before start of infusion)	X1	X
End of modakafusp alfa infusion (\pm 10 minutes)	X1	X
2-4 hours after end of modakafusp alfa infusion	X1 ^b	X ^b
Total Timepoints	3	

PK: pharmacokinetic(s).

^a The timing of the morning visits should occur at approximately the same time as previous dosing days. The date/time of the start and end of infusions should be recorded accurately. PK samples should only be collected from the contralateral arm and not from the drug infusion arm.

^b Cycles 1, 3, and 5 only.

^c Blood samples for pembrolizumab PK will only be collected at the visits with pembrolizumab dosing (ie, Cycle 1, Cycle 3, Cycle 5, Cycle 7 and beyond).

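### The phase 2 schedule footnote sets the Cycle 3+ infusion-reaction watch before the end of infusion; section 8.8.1 and the phase 1b footnote set it after

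*Protocol*

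**What the plan says.** The protocol states the observation rule for infusion-related reactions three times in current text.

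- **Section 8.8.1 (Premedication)**, not limited to one phase. For Cycles 1 and 2: "During the infusion and for 6 hours post-infusion in the first 2 treatment cycles". After that: "In Cycle 3 and beyond, patients should be continually monitored for at least 2 hours post the end of infusion".
- **Footnote c, phase 1b schedule (Tables 16.a to 16.c)**, for Cycle 3 onward: "patients should be continually monitored for at least 2 hours after the end of infusion".
- **Footnote c, phase 2 schedule (Tables 16.d and 16.e)**, attached to the vital signs row. For Cycles 1 and 2: "During the first infusion and for 6 hours postinfusion in the first 2 treatment cycles". After that: "In Cycle 3 and beyond, patients should be continually monitored for at least 2 hours before the end of infusion".

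Two other places bear on which text a phase 2 site will follow. The combination-cohort paragraph of section 8.1 says: "Please see premedication and observation guidelines in Section 8.8.1". Section 9.3 says: "Sites will make every effort to see patients in the clinic to complete all study-specified assessments as outlined in the SOE", and it refers sites to the same schedule for the timing of assessments. Section 9.3.7 likewise takes the timing of vital signs from Appendix A.

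**The concern.** The phase 2 footnote puts the observation period on the wrong side of the end of infusion. A site working from the schedule alone would see no requirement to keep a patient under continual observation once the infusion stops, from Cycle 3 on. It could release the patient before the 2 hours that section 8.8.1 requires.

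Sections 8.10.1 and 10.2.1.1 designate infusion-related reactions as an adverse event of special interest and say they can develop during the infusion or shortly after it. The period just after the infusion is the part the wording loses.

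The same footnote departs from section 8.8.1 a second time. By referring to the first infusion rather than the infusion in each of the first two cycles, it omits continual monitoring during the Cycle 2 infusion if read literally.

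The stake is patient safety at the site. The estimates and decision rules are not affected.

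**Working it through.** **1. The rule side by side**

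| Source | Cycles 1–2 | Cycle 3 onward |
|---|---|---|
| Section 8.8.1 (both phases) | During the infusion, plus 6 h after | At least 2 h after the end |
| Phase 1b footnote c | During the infusion, plus 6 h after | At least 2 h after the end |
| Phase 2 footnote c | During the *first* infusion, plus 6 h after | At least 2 h *before* the end |

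Two of the three agree. The third differs in one word for Cycle 3 onward and in one added word for Cycles 1–2.

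**2. What the literal phase 2 wording requires**

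Section 8.1 gives the infusion length: 1 hour below 1.5 mg/kg, and 2 hours at 1.5 mg/kg or more, extendable to 4 hours. The start of the period, measured from the start of infusion, is the infusion length minus 2 hours:

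- 1-hour infusion: 1 − 2 = −1 h, so it begins an hour before the drug.
- 2-hour infusion: 2 − 2 = 0 h, so it is the infusion itself.
- 4-hour infusion: 4 − 2 = 2 h, so it covers only the second half.

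In every case the required continual time after the infusion is 0 h, against at least 2 h in section 8.8.1.

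**3. Is it a slip?**

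Almost certainly. The preceding sentence of the same footnote sets a post-infusion period for Cycles 1–2, and the parallel phase 1b footnote says *after*.

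**4. In which cycles would sampling keep a patient on site anyway?**

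Phase 2 samples from Cycle 3 on that are due at a nominal 2 h or later after the infusion:

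- Cycle 3: PK at 2–4 h in expansion (Table 16.h) and at 2 h and 6 h in the lead-in (Table 16.g); biomarkers at 4 h (Table 16.d, footnote q).
- Cycle 5: PK at 2–4 h in expansion, where Table 16.h footnote b limits this sample to "Cycles 1, 3, and 5 only"; PK at 2 h in the lead-in.
- Cycles 7 and 15: biomarkers at 4 h (Table 16.e, footnote q).

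That is 4 cycles. In the others the last Day 1 PK sample is at the end of infusion.

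- Cycles 3 to 15: 15 − 3 + 1 = 13 cycles; 13 − 4 = 9 with no later same-day sample.
- Two-year maximum, assuming no delays: 104 weeks at one dose every 3 weeks gives doses in weeks 0 to 102, so 102 / 3 + 1 = 35 cycles. From Cycle 3: 35 − 2 = 33; 33 − 4 = 29 with no later same-day sample.

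These counts show where the schedule gives no incidental backstop. They do not measure early releases or harm.

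**5. What the reaction data can and cannot say**

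Sections 4.3.2.2 and 4.3.3 report infusion-related reactions in 8 of 17 patients (8/17 = 47.1%), all Grade 2, and serious in 7 (7/17 = 41.2%). These are single-agent phase 1b patients with a median of 2 cycles, and the events are not split by cycle. Section 8.8.1 cites them as the reason premedication became mandatory. They show that the reaction matters for this drug, but they do not estimate its frequency from Cycle 3 in phase 2.

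**The case against.** The strongest reply is that the correct rule is already in the body of the protocol and that phase 2 sites are sent to it. Section 8.1 refers the combination cohorts to section 8.8.1 for observation, nothing gives a footnote precedence over that section, and the footnote sets a minimum without permitting early release. A site can satisfy both texts by following section 8.8.1. This stands, and it is why the error is not a fatal flaw. It does not remove the conflict, because section 9.3 sends sites to the schedule for timing and the footnote sits on the row staff use on infusion day.

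Other protections also remain:

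- Footnote c keeps vital signs after the infusion, blood pressure every 30 minutes in the first 4 infusions, and a hold on release after hypotension.
- Section 8.10.1 asks for careful monitoring during infusions, with resuscitation equipment at the bedside. This softens the Cycle 2 point considerably: that infusion is not left unwatched.

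None of these sets a 2-hour observation period after the infusion.

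Two further points are fair. On pembrolizumab days, the hour before a 1-hour modakafusp alfa infusion is largely taken up by the pembrolizumab infusion and the 30-minute gap, so the literal period is feasible then, though still not the one intended. The phase 2 dose is not stated, so the 1-hour case may not arise. Finally, a missing late sample does not show that a patient left early.

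**Conclusion.** The inconsistency is real and the phase 2 footnote is wrong as written. It should be fixed. It is a wording conflict between sections rather than a deliberate design choice.

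Its reach is limited to phase 2 patients who get to Cycle 3 (plus the Cycle 2 infusion for the second phrase). Their number is not given; the planned phase 2 ceiling is 84. For them, 9 of the 13 cycles from 3 to 15, and every cycle from 16 on, have no late same-day sample. The 29-of-33 figure rests on the assumption of 35 undelayed three-week cycles, which few patients may complete. No risk of a missed reaction can be calculated from the documents. Harm would require a site to rely on the footnote without consulting section 8.8.1. Confidence that the text needs correcting is high.

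**What to change.** In footnote c of Tables 16.d and 16.e, make two changes so that it matches section 8.8.1:

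- Replace *before* with *after* in the Cycle 3 onward sentence.
- Delete *first* from the Cycles 1–2 sentence, so that monitoring during infusion covers both cycles.

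Send sites a clarification letter now and carry the correction into the next amendment. The cost is two phrases and one letter. It adds no observation time beyond what section 8.8.1 already requires and does not change the analysis or the sample size.
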